1.2 Study Design

Study AMAX is a long-term study of participants completing Studies I6T-MC-AMAM (Study AMAM) and I6T-MC-AMAG (Study AMAG) (see schema below).

Two intervention groups will be studied in participants with moderate-to-severe CD:

Mirikizumab CCI

Mirikizumab CCI

Q4W; CCI

Q4W; CCI

Q4W; 900 mg is the induction dose being studied in Study AMAM.

Study participants will receive mirikizumab for an extended period of time (approximately 3 years or until commercial availability of mirikizumab, whichever comes first) and then enter a 12- to 16-week posttreatment follow-up period. After completion of the long-term extension period, if mirikizumab is not yet locally commercially available and reimbursable, eligible participants will be provided with an option of continued access to open-label mirikizumab, and then enter CCI follow-up period

Study AMAM participants will require an endoscopy to be performed at Week 52, CCI

Study AMAM participants will require an endoscopy to be performed at Week 52, CCl visit occurs more than 16 weeks after the last endoscopy in Study AMAX.

Study AMAG participants who are entering Study AMAX after completing CCI into Study AMAX.

Participants who have not yet completed CCI

Study intervention may be permanently discontinued or temporarily withheld during the study (see Sections 7.1.1 and 7.1.2 of the AMAX Protocol). Participants who permanently discontinue study drug early will undergo early termination procedures, which include an early termination visit (ETV) and post-treatment follow-up visits (V801 and V802).

No rescue medication is allowed during the study. Participants who enter Study AMAX on corticosteroids should initiate corticosteroid tapering as described in the protocol (see Section 6.5.3 of the AMAX Protocol).

An interim analysis of the co-primary endpoints may be conducted when all Study AMAM participants complete Week 52 of Study AMAX. Additional ad-hoc interim analyses may be performed as deemed appropriate or to fulfill the need of regulatory interactions or publication purposes.

A Data Monitoring Committee (DMC) consisting of members external to Lilly will be established for interim safety monitoring across all the sponsor's adult Phase 3 studies in participants with CD. Additional details can be found in the AMAX protocol (see Section 10.1.5) and in the DMC Charter.

The final database lock will occur after the last participant has completed Study AMAX.

2 Statistical Hypotheses

This is an open-label extension study with no randomization. Participants from Study AMAM are assigned to either mirikizumab SC or mirikizumab IV followed by SC based on their endoscopy response status at Week 52 in Study AMAM. Participants from Study AMAG are assigned to mirikizumab SC. Therefore, no intervention comparisons or formal hypothesis testing will be done. Analyses and summaries will be focused on point estimates and confidence intervals.

3 Sample Size Determination

The sample size of Study AMAX will be determined by the number of participants who enroll in Study AMAX from the preceding studies (Study AMAM and Study AMAG). It is anticipated that approximately 50% to 70% of the eligible participants will be enrolled from Study AMAM and Study AMAG. Based on this assumption, 640 to 900 participants are expected to enter Study AMAX.

4 Analysis Sets

For purposes of analysis, the analysis sets are defined in the table below.

Population	Description	
Modified Intent-to-	Definition: All enrolled participants who take at least 1 dose of study	
Treat (mITT)	intervention, even if the participant does not receive the correct study	
Population ¹	intervention, or otherwise does not follow the protocol. Participants	
	will be analyzed according to the assigned treatment arms described in	
	Section 5.1.4.	
	Purpose: Used for sensitivity analyses of efficacy, health outcomes	
	and quality of life measures.	
Primary Analysis	Definition: All patients from the mITT population who	
Set (PAS)		
Population ¹	Purpose: Used for primary analyses of efficacy, health outcomes and	
	quality of life measures.	
Safety Population ¹	Definition: Same as mITT Population.	
	Purpose: Safety analysis will be conducted on this population.	
Sub-Populations ^{1,2}	Definition: All participants in the PAS (or mITT or Safety) population	
of PAS (or mITT or	who meet the criteria for the endpoints being examined (an example,	
Safety)	the study primary endpoint, the endoscopic response at Week 52 in	
	AMAX, a subset population will be the endoscopic responders at Week	
	52 of the originating study). Participants will be analyzed according to	
	the assigned treatment arms described in Section 5.1.4.	
	Purpose: Used for efficacy, health outcomes, quality of life measures	
	and may be used for safety analysis.	

¹ For early interim analysis where not all participants could have completed the time point of interest, participants who enrolled in AMAX after a specified date will be excluded from the analysis to ensure that all patients in the analysis could have completed the time point of interest.

² When defining the subpopulation of interest, concomitant medication related intercurrent events in AMAM will not be considered. For example, a patient who violated specified concomitant medication rules would be considered as an endoscopic non-responder in AMAM due to the intercurrent event, but could still considered a responder in AMAX due to directly looking at the endoscopic data.

5 Statistical Analyses

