6.5.3. Corticosteroid Taper

For participants who enter AMAX on corticosteroids, corticosteroid tapering as described below should be initiated or continued for participants who at the discretion of the investigator have achieved clinical response at Week 12. Instructions regarding guidance for use are detailed in Section 10.8, Appendix 8. For participants who cannot tolerate the corticosteroid taper without recurrence of clinical symptoms, corticosteroid taper may be paused and/or corticosteroid dose may be increased up to the original dose at baseline. The oral corticosteroid dose, however, may not be increased above the baseline dose in originator study unless due to medical necessity.

For participants who previously have tapered off corticosteroids but have recurrence of symptoms during study AMAX necessitating reintroduction of corticosteroids, this is allowed, however the dose may not be increased above the baseline dose in originator study, unless due to medical necessity.

Additionally, for participants who were not on oral corticosteroids during the originator study, oral corticosteroids may not be initiated, unless due to medical necessity.

For participants who have not begun corticosteroid tapering at Week 12 or participants who start corticosteroids after Week 12, tapering should be considered over the course of the study as soon as the participant demonstrates clinical response. Investigators must contact the Study Medical Monitor to discuss any participant who does not initiate CS tapering upon achieving clinical response.

The recommended tapering schedule for oral corticosteroids (other than budesonide) is as follows; however, investigators may taper steroids as clinically feasible and appropriate:

- Dose >10 mg/day prednisone or equivalent: taper daily dose by 5 mg/week until receiving 10 mg/day, and then continue tapering at 2.5 mg/week until 0 mg/day.
- Dose ≤ 10 mg/day prednisone or equivalent: taper daily dose by 2.5 mg/week until 0 mg/day.

For participants receiving oral budesonide, the recommended tapering schedule is having their dose tapered by 3 mg every 3 weeks until 0 mg/day.

6.7. Management of Hypersensitivity, Infusion-Related Events, Infusion Site Reactions, and Injection Site Reactions

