10.7. Appendix 7: Prohibited Medications

This section outlines medications that are prohibited during both the originator studies and the AMAX study. Use of the medications listed in this appendix is allowed at the discretion of the investigator after a participant discontinues study drug and completes the ETV.

Drug Class	Guidance for Use
The following medications are prohibited throughout duration of study:	
Anti-TNF antibodies (for example, infliximab, adalimumab, or certolizumab pegol)	Prohibited throughout duration of study.
Anti-integrin antibodies:	
Natalizumab	Prohibited throughout duration of study.
Other anti-integrin antibodies (for example, vedolizumab)	Prohibited throughout duration of study.
Agents depleting B or T cells (for example, rituximab, alemtuzumab, or visilizumab)	Prohibited throughout duration of study.
Immunomodulatory medications, including oral cyclosporine, IV cyclosporine, tacrolimus, mycophenolate mofetil, thalidomide, or JAK inhibitors (other than topical)	Prohibited throughout duration of study.
Rectally administered 5-ASA therapies (enemas or suppositories)	Prohibited throughout duration of study.
Rectally administered corticosteroids (enemas or suppositories)	Prohibited throughout duration of study.
Corticosteroids	
A course of IV corticosteroids is prohibited throughout duration of study, except for use as premedication for infusion or for short-term treatment of acute non-CD events (for example, allergic reactions). IV corticosteroids used for CD may result in discontinuation, therefore consult your medical monitor.
 
From Week 0 to Week 12, initiation or adjustment of systemic corticosteroids for non-CD indications is prohibited unless needed due to AEs or for appropriate medical management.
 
After Week 12, participants may transiently initiate or increase doses (that is, for <4 weeks) of corticosteroids for reasons other than loss of response to treatment for CD (for example, premedication for infusions, and stress doses of corticosteroids for surgery, asthma, and allergic reaction).
 
Locally administered corticosteroids (for example, inhaled, intranasal, intra-articular, or topical) are allowed.
 
Systemic corticosteroid use is allowed for adrenocortical insufficiency (Section 6.5 and 6.7.1).

Any investigational therapy (biologic or nonbiologic)	Prohibited throughout duration of study.
Interferon therapy	Prohibited unless medically necessary for short-term COVID treatment

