1.1 Objectives and Endpoints

Estimands for the co-primary and secondary endpoints are defined as follows:

- Population: Primary Analysis Set (PAS) and specified sub-population (Section 4)
- Intercurrent-event strategies (IES):
 - o For binary endpoints, a hybrid estimand strategy is used. For ICEs of study treatment discontinuation for reasons other than commercial availability and extraordinary circumstances including study treatment supply issues and site termination, the composite strategy will be used where participants with these ICEs are classified as non-responders subsequent to discontinuation. To handle the ICE of study treatment discontinuation due to commercial availability and extraordinary circumstances including study treatment supply issues and site termination, the hypothetical scenario where these patients remained on study treatment is envisaged as the target of estimation (see details on imputation in Section 5.1.5).
 - o For continuous endpoints a hybrid estimand strategy is used. For ICEs of study intervention discontinuation for reasons other than commercial availability and extraordinary circumstances including study treatment supply issues and site termination, the composite strategy will be used such that measurements after the ICEs will return to baseline. To handle the ICE of study treatment discontinuation due to commercial availability and extraordinary circumstances including study treatment supply issues and site termination, a hypothetical scenario is envisaged in which these patients remained for the rest of the study and measurements after this ICE will be imputed (see details imputation in Section 5.1.5).
- Population level summary (PLS):

[figure not shown]
o Binary endpoints: proportions

o Continuous endpoints: LS mean

Objectives and Endpoints

Objectives	Endpoints
Primary	
CCI	
To assess the effect of mirikizumab on clinical remission by CDAI and endoscopic response a	Proportion of participants achieving clinical remission by CDAI (CC) at Week 52 of AMAX

Objectives	Endpoints
	Proportion of participants achieving endoscopic response (defined by CC) in SES-CD Total Score) at Week 52 of AMAX
Secondary	

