	Clinical remission by CDAI	Descriptive analysis with NRI	PAS – In participants with clinical remission by CDAI at W52 of originating study PAS – In participants without clinical remission by CDAI at W52 of originating study	All visits with measurements in Complete Study Period
		Descriptive analysis with NRI, mNRI and as Observed	PAS	All visits with measurements in Complete Study Period

		Analysis Method	Population	
Measure	Variable	(Section 5.1.1)	(Section 4)	Time Point(s)
	Clinical response by CDAI	Descriptive analysis with NRI, mNRI and as Observed	PAS	All visits with measurements in Complete Study Period
	CDAI total score	Descriptive analysis with mBOCF and as Observed	PAS	All visits with measurements in Complete Study Period
	Change from baseline in CDAI total score	Descriptive analysis with ANCOVA and as Observed	PAS	All visits with measurements in Complete Study Period
	AP average	Descriptive analysis with mBOCF and as Observed	PAS	All visits with measurements in Complete Study Period
	Change from baseline in AP average	Descriptive analysis with ANCOVA and as Observed	PAS	All visits with measurements in Complete Study Period
	SF average	Descriptive analysis with mBOCF and as Observed	PAS	All visits with measurements in Complete Study Period
	Change from baseline in SF average	Descriptive analysis with ANCOVA and as Observed	PAS	All visits with measurements in Complete Study Period
Composite SES-CD and CDAI endpoints	Clinical remission by CDAI and endoscopic response	Descriptive analysis with NRI, mNRI, and as Observed	PAS – In participants with Clinical Remission by CDAI and Endoscopic Response at Week 52 of the Originating study	All visits with measurements in Complete Study Period

		Analysis Method	Population	
Measure	Variable	(Section 5.1.1)	(Section 4)	Time Point(s)
Measure Corticosteroid Free	Corticosteroid free Clinical Remission by CDAI	(Section 5.1.1) Descriptive analysis with NRI, mNRI, and as Observed	PAS – In participants taking corticosteroids at baseline and with CS free clinical remission by CDAI at W52 of originating study PAS – In participants taking	All visits with measurements in Complete Study Period
			corticosteroids at baseline and who did not achieve CS free clinical remission at CDAI at W52 of originating study	

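### The SAP's no-rescue statement conflicts with protocol 6.5.3, and no visible supplementary analysis shows how far added corticosteroids contribute to the CDAI co-primary across the primary analysis set

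*SAP*

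**What the plan says.** **On rescue and corticosteroids.** SAP 1.2 says "No rescue medication is allowed during the study", and continues: "Participants who enter Study AMAX on corticosteroids should initiate corticosteroid tapering as described in the protocol", citing protocol 6.5.3. That protocol section is more permissive than the first sentence. Of participants who had tapered off and then relapse, it writes: "recurrence of symptoms during study AMAX necessitating reintroduction of corticosteroids, this is allowed, however the dose may not be increased above the baseline dose" (the originator-study dose), with an exception for medical necessity. For participants not on oral corticosteroids in the originator study, it says "oral corticosteroids may not be initiated, unless due to medical necessity". Protocol Appendix 7 prohibits a course of IV corticosteroids, but adds "IV corticosteroids used for CD may result in discontinuation, therefore consult your medical monitor", so stopping study drug is not automatic.

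**On the estimand.** For binary endpoints, SAP 1.1 applies the composite (nonresponder) strategy as follows: "For ICEs of study treatment discontinuation for reasons other than commercial availability and extraordinary circumstances". Discontinuation for the excepted reasons is handled hypothetically. SAP 5.1.5 repeats this. The nonresponder list in protocol 9.4.1.4 has three entries: endpoint not met, data missing, treatment stopped. None of these places mentions corticosteroids.

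**On steroid-free remission.** SAP Appendix 1 defines it as a separate variable: CDAI remission plus at least 12 weeks off corticosteroids. SAP Appendix 2 analyses it in two rows. One is "In participants taking corticosteroids at baseline and with CS free clinical remission by CDAI at W52 of originating study"; the other covers baseline users who had not achieved it. Under SAP 5.1.2, baseline for efficacy is the originating study's baseline unless stated otherwise.

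**The concern.** The trial is open-label and uncontrolled, and its output is point estimates with confidence intervals. A Week 52 remission rate will be read as what continued mirikizumab achieves. If some remitters got there with corticosteroids added after a relapse, the rate describes mirikizumab plus corticosteroids as needed. That is a legitimate quantity to estimate, but the SAP does not say it is the one being estimated, and its design summary tells the reader that rescue does not occur. The reader also needs some analysis that shows how much the choice matters.

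**Working it through.** The plan states no figure on this point, so there is none to reproduce. The check is first of text, then an illustration of size.

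**Text.**

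1. Is corticosteroid use after a relapse possible while study drug continues? Yes, under protocol 6.5.3, by reintroduction or, for medical necessity, by a higher dose or a new start.
2. Does such use make the participant a nonresponder? No. Only discontinuation does so (SAP 1.1 and 5.1.5; protocol 9.4.1.4).
3. Does CDAI remission itself carry a steroid condition? The threshold is blacked out, but the eight CDAI items in SAP Appendix 7 do not include corticosteroids, and steroid-free remission is defined as CDAI remission plus a steroid condition. Plain CDAI remission therefore has none.
4. Does a planned supplement to the co-primary change this? SAP 5.3.3 lists modified nonresponder imputation, observed cases and the mITT population. SAP 5.7.2 lists biologic-failed and not-biologic-failed subgroups. None alters how corticosteroid use is counted.
5. Whom do the steroid-free rows cover? Originating-study baseline users only. Someone who restarts after a taper was probably such a user and is covered. A participant who first starts corticosteroids in AMAX is in neither row.

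**Size, under assumptions.** Let p be the CDAI remission rate as planned and s the share of remitters with corticosteroids started, restarted or increased for CD. Counting them as nonresponders lowers the rate by p × s.

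- Group size n: protocol 2.2.5 gives 220 of 579 AMAM mirikizumab participants meeting the composite that includes Week 52 endoscopic response. With all of them, or the 70% or 50% entry anticipated in protocol 9.2, n = 220, 154 (0.70 × 220) or 110 (0.50 × 220). This is an anchor only; n affects the drop only through rounding to whole participants.
- p = 70%, 80% or 90%, and s = 2%, 5% or 10%: assumed.

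The extremes are 0.70 × 0.02 = 1.4 points and 0.90 × 0.10 = 9.0 points. With whole participants, the smallest drop is 2/154 = 1.3 points and the largest is 20/220 = 9.1 points.

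For n = 220 and p = 80%, the Wilson 95% interval has centre (p + z²/2n)/(1 + z²/n) and half-width z√[p(1−p)/n + z²/4n²]/(1 + z²/n), with z = 1.96:

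| Remitters reclassified | Remission | Wilson 95% interval |
|---|---|---|
| none (as planned) | 176/220 = 80.0% | 74.2 to 84.8 |
| 2% (4) | 172/220 = 78.2% | 72.3 to 83.1 |
| 5% (9) | 167/220 = 75.9% | 69.8 to 81.1 |
| 10% (18) | 158/220 = 71.8% | 65.5 to 77.3 |

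The planned interval has a half-width of about (84.8 − 74.2)/2 = 5.3 points. At s = 5% the shift of 4.1 points is smaller than that; at s = 10% the shift of 8.2 points exceeds it.

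**The case against.** The strongest reply is that this is a deliberate estimand choice. The SAP's event list matches protocol 9.4.1.4. SAP Section 4, footnote 2, shows that the authors had concomitant-medication events in mind, and SAP 1.2 itself refers the reader to protocol 6.5.3. The residual group is also narrow: new oral starts need medical necessity, and under protocol 6.5.2 participants who need a prohibited drug should generally stop study drug, which makes them nonresponders. Those points stand, and they are why the co-primary need not change. They do not supply an analysis that shows the effect of the choice.

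The objection also rules out several stronger readings that a reader might infer:

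- **That relapses treated with corticosteroids count as remission because the steroid-free rows are limited to baseline users.** The direct cause is that the estimand has no corticosteroid event. The restriction only limits which cases the steroid-free rows can show, and most who restart after a taper are probably inside it.
- **That the SAP derived its event list from the no-rescue sentence.** No text links the two.
- **That new starters appear in no planned analysis at all.** Some objectives and endpoint text are blacked out, the SAP does not define rescue medication, and supplemental SAPs are foreseen. The claim can cover visible text only. Protocol 9.4.2.3 also summarises concomitant medication by group, though not crossed with remission.
- **That the gap between plain and steroid-free remission equals the part owed to added corticosteroids.** The 12-week definition also removes stable users, those still tapering and, as written, those taking corticosteroids for other conditions.

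**Conclusion.** The point holds in a limited form. The SAP 1.2 sentence and protocol 6.5.3 contradict each other and must be reconciled; which rule is right is not a matter for this review. As planned, a participant given added corticosteroids for CD who stays on mirikizumab and meets the Week 52 threshold is a co-primary remitter under the main analysis, and no visible supplementary analysis shows the effect in the whole PAS.

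The size is unknown. The 1.3 to 9.1 points rest on assumed remission of 70% to 90% and an assumed 2% to 10% of remitters affected. The drop would be nil if no remitter had such use. No hypothesis test is at stake, so the consequence is for interpretation of a descriptive rate.

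**What to change.** 1. Reword SAP 1.2 and protocol 6.5.3 so that they agree, and state in SAP 1.1 that corticosteroid use does not affect responder status in the co-primary, if that is the intention.
2. Leave the co-primary unchanged and add two analyses to SAP 5.3.3 and Appendix 2:
   - (a) corticosteroid-free clinical remission by CDAI, using the existing Appendix 1 definition, in all PAS participants in the co-primary analysis group, whatever their baseline corticosteroid use;
   - (b) the CDAI co-primary with corticosteroid start, restart or increase for CD before Week 52 counted as nonresponse.

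Analysis (b) is needed because (a) mixes added corticosteroids with stable, tapering and non-CD use.

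The cost is SAP wording, one further run of an existing derivation for (a), and one new flag for (b). Protocol 6.5 already requires concomitant medication, including that for CD, to be recorded. The flag assumes that start date, dose and indication can be read from those records. Analysis (b) is strict: someone who restarted early and was off corticosteroids again well before Week 52 still counts as a nonresponder, so it should be read beside (a). The downside is that a second, lower remission figure is reported. This is a cheap improvement.

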2.3. Benefit/Risk Assessment

At the time of the last benefit/risk assessment, evaluation of unblinded safety data from the completed or ongoing clinical studies has not revealed any dose-related safety or tolerability concerns. Mirikizumab has demonstrated efficacy in blinded, placebo-controlled Phase 2 and Phase 3 studies in psoriasis (Reich et al. 2019; Papp et al. 2020), Phase 2 and 3 studies in UC (Sandborn et al. 2018; D'Haens et al. 2023), and Phase 2 and Phase 3 studies in CD (Sands et al. 2022; Ferrante et al. 2024). Evaluation of unblinded safety data in studies in psoriasis, UC, and CD with dose regimens of up to 1000 mg IV Q4W for up to 52 weeks and up to 300 mg SC Q4W for up to 104 weeks have shown a safety profile generally consistent with the IL-23 antibody class. These data are summarized in the IB. Given the data from the Phase 2 and Phase 3 studies in CD and data from other clinical studies completed to date, potential benefits to participants who receive mirikizumab while participating in Study AMAX are reasonably anticipated.

In Phase 2 mirikizumab studies where mirikizumab in a lyophilized solution was administered intravenously over no less than 30 minutes, immediate hypersensitivity reactions, including 2 reports of immediate, infusion-related hypersensitivity events consistent with anaphylaxis and AEs that resulted in study drug discontinuation, were reported. In response, the duration of mirikizumab administration was increased. After this change was implemented, no additional events consistent with anaphylaxis were reported, and no anaphylactic reactions have been reported in participants who received the current Phase 3 formulation of mirikizumab (planned for commercial use). Infusion-related hypersensitivity reaction is an ADR for mirikizumab. Based on unblinded Phase 3 data, the following additional ADRs have been identified: injection site reactions, upper respiratory tract infections, alanine amino transferase increased, aspartate aminotransferase increased, headaches, and rashes. Consult the IB for information regarding ADRs and potential risks with mirikizumab.

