5.6 Safety Analyses

In general, safety evaluations will be based on the Safety Population for the Induction Period and Complete Study Period. Select safety analysis will also be performed for the continued access period as needed.

For the purpose of Study AMAX alone, the following are planned:

- Listing of Serious Adverse Events (SAEs)
- Listing of adverse events leading to permanent discontinuation of study drug
- Summary of SAEs (with different columns for the intervention groups specified in Section 5.1.4)
- Summary of AEs leading to permanent discontinuation of study drug (with different columns for the intervention groups specified in Section 4)

The safety data from this study will also be used as part of ongoing safety reviews. The safety data from this study will also be used as part of integrated summaries in submissions/disclosures and ongoing safety review through study end.

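### Safety and exposure summaries follow the assigned AMAX arm even when a different route was given; the plan has no treatment-received rule (minor, and only if a dosing error occurs)

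*SAP*

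**What the plan says.** SAP Section 4 defines mITT as enrolled participants with at least one dose of study "intervention, even if the participant does not receive the correct study" intervention, and says that they "will be analyzed according to the assigned treatment arms described in" Section 5.1.4. The Safety row reads "Definition: Same as mITT Population", and adds "Purpose: Safety analysis will be conducted on this population". The sub-population row, which expressly covers subsets of the Safety set, again refers to "the assigned treatment arms described in Section 5.1.4".

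SAP Section 2 describes the assignment: "Participants from Study AMAM are assigned to either mirikizumab SC or mirikizumab IV followed by SC", according to Week 52 endoscopic response in AMAM. AMAG participants are all assigned to SC.

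SAP 5.1.4 gives one list of groups for the PAS, mITT and Safety sets, split into SC and IV within each AMAM treatment sequence. SAP 5.6 uses it for the "Summary of SAEs (with different columns for the intervention groups specified in Section 5.1.4"). For AE discontinuations (5.6) and participant-years (5.6.1) the SAP points to Section 4 for the groups. Section 4 lists no groups, only the assigned-arm rule.

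Protocol 9.3 agrees: Safety equals mITT, mITT is drawn from ITT, and ITT is analysed by assigned treatment.

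**The concern.** Safety tables are normally read as what happened to people who were given a regimen. Here they describe people for whom a regimen was intended. In a randomised trial, analysis as assigned preserves the randomised comparison. AMAX is not randomised and makes no intervention comparisons (SAP Section 2), so there is no such comparison to preserve.

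Route matters for safety in these documents. Protocol 2.3 states "Infusion-related hypersensitivity reaction is an ADR for mirikizumab". Protocol 4.3 reports more SAEs with 1000 mg IV in AMAG, including two infusion events consistent with anaphylaxis; protocol 2.3 adds that none followed after the infusion was lengthened. SC versus IV is therefore the split where a misplaced event would mislead most. At stake are the SAE and AE-discontinuation summaries, the exposure totals, and the registry AE tables by intervention group (SAP 6.6).

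**Working it through.** The plan gives no figure to reproduce. The check is a trace through the text, followed by an illustration of size.

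**Trace of the rule**

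1. SAP Section 4: Safety = mITT; mITT keeps wrongly treated participants and uses assigned arms.
2. SAP 5.1.4: the groups for the Safety set are separate SC and IV columns.
3. SAP 5.6 and 5.6.1: these groups, or Section 4 itself, define the columns for SAEs, AE discontinuations and participant-years.
4. Search for an offsetting rule: the intervention received is used only for the originating study (SAP 5.1.1; protocol 9.4.1). SAP 6.5 lists deviations from the dosage regimen but moves nobody to another column. Neither document has a treatment-received rule for AMAX.

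Two consequences follow. A participant assigned to SC and infused in error stays in the SC column, with any resulting event. A participant assigned to IV who only ever receives SC adds SC-only exposure to the IV denominator.

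**Size of one misplaced event**

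Take a column of n participants with one participant wrongly in it who had an SAE, and x other participants with SAEs. The shift in the column percentage is

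(x + 1)/n − x/(n − 1) = 1/n − x/[n(n − 1)],

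which is at most 1/n.

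The documents give neither column sizes nor an error rate, so n is assumed:

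- n = 25 (assumed): 1/25 = 4.0 points.
- For the placebo/placebo/SC column, a rough ceiling comes from protocol 2.2.5: 18 of 199 AMAM placebo participants had both PRO response at Week 12 and endoscopic response at Week 52. With n = 18, 1/18 = 5.6 points.
- Applying the overall 50% to 70% enrolment assumption (SAP Section 3): 18 × 0.5 = 9 and 18 × 0.7 = 12.6, about 13. Then 1/9 = 11.1 points and 1/13 = 7.7 points.

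The second and third lines assume that only Week 12 PRO responders stayed on placebo, that SC assignment required endoscopic response, and that the overall enrolment fraction applies to this subgroup. The count of 18 is itself approximate, because SAP Section 4 ignores AMAM concomitant-medication events when it defines responders.

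With no dosing error, the shift is 0 in every column.

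**The case against.** The case against making this change has real force on several points.

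- **The scenario is remote.** IV product comes in vials and SC product in prefilled syringes (protocol 6.1), so a route error needs the wrong presentation. No such error is reported. This stands.
- **The event would not be hidden.** SAEs and AE discontinuations are listed individually (SAP 5.6), dosing deviations are listed (SAP 6.5), and adverse events of special interest carry extra data collection (protocol 8.3.7). The pooled AMAM and Total columns do not depend on the SC/IV split. Protocol 9.4.4 places the main weight on integrated safety summaries. This stands and limits the effect.
- **The columns are not pure route columns.** The IV arm is IV followed by SC, so it already contains SC-phase events and long SC exposure. This weakens the IV column as a route summary. It does not help the SC column, which is meant to contain no infusions.
- **Assigned arm carries information.** For AMAM participants it reflects Week 52 endoscopic response, so reclassification mixes response states within a column. It would therefore be wrong to infer that analysis as assigned serves no purpose. The answer is to footnote reclassified participants.
- **A rule may exist elsewhere.** The table specifications are in a separate document (SAP Section 1) that was not available here. They should not contradict SAP Section 4, which states the assigned-arm rule explicitly.

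A reader might infer that infusion events are in fact being counted as SC events, or that a wrong assignment produces this. The documents support neither. No misplaced dose is described. A participant wrongly assigned to IV and infused would be counted under IV. The problem arises only when the dose given differs from the assigned arm.

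**Conclusion.** The point holds as a minor defect in a stated rule. Both documents tie safety summaries to the assigned AMAX arm, and nothing in either moves a participant who received a different route. The consequence is conditional on a dosing error. Given one misplaced participant with an SAE, the affected column shifts by at most 1/n: 4 points at an assumed n of 25, and about 6 to 11 points in the smallest column on the assumptions above. Pooled columns, the listings and all efficacy results are unaffected. It does not threaten the study's conclusions. It is worth settling before the final database lock, because reclassifying a participant after an infusion event has been seen would look post hoc.

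**What to change.** In SAP Section 4, keep the Safety population as all dosed participants, and state that safety and exposure summaries use the AMAX regimen actually received. Add a rule for route errors:

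- A participant assigned to SC who receives an IV dose in error, at any visit, is classified or flagged as IV-exposed from that dose. State how exposure is split at that date and whether the participant enters both denominators. A rule based on the first dose alone would miss later errors.
- A participant assigned to IV who never receives an IV dose is classified as SC.

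Footnote every reclassified participant with the assigned arm, because the SC and IV columns also reflect AMAM Week 52 endoscopic response. Keep assigned arms for efficacy.

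Align SAP 5.1.4, 5.6 and 5.6.1, so that the AE-discontinuation and exposure summaries point to 5.1.4 rather than Section 4. Align protocol 9.3 as well, or record the departure in SAP 6.3, which now reads as not applicable. Protocol 9.4.1 asks for an amendment only when a principal feature changes; otherwise the change and its justification go in the study report.

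The cost is a few sentences, plus slight mixing of response status in a column if anyone is reclassified. SAP 6.5 derives doses from the Exposure eCRF page; confirm that the page also captures route, since the SAP does not say so.
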